6.9 Efficacy Analysis

Each one of the three efficacy variables (R-MOAS, CGI-I and CGI-S) will be listed and summarized by group of the optimized dose.

6.10 Quality of Life Analysis

The quality of life endpoints CHQ-PF28, PSI-4-SF subscales (Parental Distress, Parent-Child Dysfunctional Interaction and Difficult Child), and SIPA subscales (Adolescents Domain, Parent Domain, Adolescent-Parent Relationship Domain, Life Stressors Scale and Index of Total Parenting Stress) will be listed and summarized by group of the optimized doses (<18 mg/day; 18-24 mg/day, 24-36 mg/day or 36-54 mg/day) the subject received.

Socio-demographic variables will be presented as a listing and summaries will be tabulated using descriptive statistics.

6.11 Pharmacogenomic Analysis

Individual data will be presented as a listing and summaries will be tabulated using descriptive statistics. The pharmacogenomic report may be a stand-alone document.

6.12 Sample Size and Power Considerations

There is no consideration for power or sample size determination in this open label study. The present study is an extension to the double-blind randomized 801P301, 810P302, 810P503 and 810P204 studies for the purpose of evaluating long term safety of SPN-810.

7 DOCUMENTATION

7.1 Adherence to the Protocol

The Investigator agrees, when signing the protocol, to adhere to the instructions and procedures described within and to the principles of ICH GCP as well as all governing local regulations and principles for medical research.

The protocol, ICF, and appropriate related documents must be reviewed and approved by an IRB constituted and functioning in accordance with ICH E6 and any local regulations. Documentation of IRB compliance with the ICH and any local regulations regarding constitution and review conduct will be provided to the Sponsor.

A signed letter of study approval from the IRB must be sent to the Investigator with a copy to the Sponsor prior to study start and the release of SM to the site by the Sponsor or its designee. If the IRB decides to suspend or terminate the study, the Investigator will immediately send the notice of study suspension or termination by the IRB to the Sponsor.

Study progress is to be reported to IRB annually (or as required) by the Investigator or Sponsor, depending on local regulatory obligations. If the Investigator is required to report to the IRB, he/she will forward a copy to the Sponsor at the time of each periodic report.

7.2 Changes to the Protocol

There are to be no changes to the protocol without written approval from the Sponsor.

Any change to the protocol requires a written protocol amendment or administrative change that must be approved by the Sponsor before implementation. Amendments specifically affecting the safety of subjects, the scope of the investigation, or the scientific quality of the study require additional approval by the applicable IRBs and, in some countries, by the regulatory authority. These requirements should in no way prevent any immediate action from being taken by the Investigator, or by the Sponsor, in the interest of preserving the safety of all subjects included in the study. If an immediate change to the protocol is felt by the Investigator to be necessary for safety reasons, the Medical Monitor and IRB must be notified promptly.

Changes to the protocol, which are administrative in nature do not require formal protocol amendments or IRB approval, but the IRB must be kept informed of such changes. In these cases, the Sponsor will send a letter to the IRB detailing such changes.

7.3 Protocol Deviations

There are to be no Investigator-initiated deviations from the protocol. Any subject whose treatment deviates from the protocol or who is not qualified for study participation may be ineligible for analysis and may compromise the study. The date of and reason for deviations must be documented in all cases. Significant or major protocol deviations impacting the safety of the subject or the integrity of the study must be reported by the Investigator to the IRB immediately. Reporting of all other protocol deviations

must adhere to the requirements of the governing IRB. Protocol assessments will continue until the end of the study, unless the protocol deviations put the subject at risk or the subject's condition requires that he/she be discontinued from the study.

7.4 Data Quality Assurance

This study will be organized, performed, and reported in compliance with the protocol, standard operating procedures (SOPs), working practice documents, and applicable regulations and guidelines. Site audits may be made periodically by the Sponsor's Quality Assurance team or qualified designee, as an independent function from the study conduct team.

7.4.1 Data Collection

The primary source document will be the subject's medical record. If separate research records are maintained by the Investigator(s), both the medical record and the research record will be considered the source documents for the purposes of monitoring and auditing the study.

Electronic data collection techniques will be used to collect data directly from the study sites using eCRFs. The electronic data will be stored centrally in a fully validated clinical database.

Data recorded on source documents will be transcribed into the eCRFs in accordance with the eCRF Completion Instructions provided to the study sites. The Investigator is responsible for ensuring that all sections of each eCRF are completed correctly, and that entries can be verified against source documents. The eCRFs will be monitored for completeness and accuracy against the source documents by the CRA(s) on a regular basis. Inconsistencies between the eCRFs and source documents will be resolved in accordance with the principles of Good Clinical Practice (GCP).

At the conclusion of the clinical study, each site's eCRF data will be extracted from the clinical database, stored on a CD-ROM and sent to the respective clinical study site for archiving. A CD-ROM containing all eCRFs will be kept by the Sponsor in the Sponsor's Trial Master File.

7.4.2 Clinical Data Management

Data from eCRFs and other external data sources (e.g., laboratory data) will be entered into and/or merged within a single clinical database as specified in the data management plan. Quality control and data validation procedures will be applied to ensure the validity and accuracy of the data in the clinical database.

7.4.3 Database Quality Assurance

In accordance with the vendor's procedures, the clinical database will be reviewed and checked for omissions, apparent errors, and values requiring further clarification using computerized and manual procedures. Data queries requiring clarification will be documented and returned to the study site for resolution. Only authorized personnel will make corrections to the clinical database, and all corrections will be documented in an audit trail.

7.5 Retention of Records

The Investigator has the responsibility to retain all study “essential documents”, as described in ICH E6. Essential documents include but are not limited to the protocol, copies of paper CRFs or eCRFs, source documents, laboratory test results, SM inventory records, Investigator's Brochure, and regulatory agency registration documents (e.g., FDA form 1572, ICFs, and IRB/IEC correspondence). The investigator should take measures to prevent accidental or premature destruction of these documents. Study essential documents should be retained until at least two years after the last approval of a marketing application or after formal discontinuation of clinical development of the investigational product. These documents should be retained for a longer period, however, if required by the applicable regulatory requirements or by an agreement with the Sponsor. The Investigator must obtain written permission from the Sponsor prior to the destruction of any study document.

It is requested that at the completion of the required retention period, or should the Investigator retire or relocate, the Investigator contact the Sponsor, allowing the Sponsor the option of permanently retaining the study records.

These records must be made available at reasonable times for inspection and duplication, if required, by a properly authorized representative of the US FDA in accordance with the US 21 CFR 312.68 or other national or foreign regulatory authorities in accordance with regulatory requirements.

7.6 Auditing Procedures

In addition to the routine monitoring procedures, the Sponsor's Corporate Quality Assurance department or qualified designee may conduct audits of clinical research activities in accordance with the Sponsor's written SOPs to evaluate compliance with the principles of ICH GCP and all applicable local regulations. A government regulatory authority may also wish to conduct an inspection (during the study or after its completion). Any inspections requested by a regulatory authority must be communicated immediately by the Investigator to the Sponsor and the CRO.

All study-related records must be made available at reasonable times for inspection and duplication, if required, by a properly authorized representative of the US FDA in accordance with the US 21 CFR 312.68 or other national or foreign regulatory authorities in accordance with regulatory requirements.

7.7 Publication of Results

Any presentation or publication of data collected as a direct or indirect result of this trial will be considered as a joint publication by the Investigator(s) and the appropriate personnel at the Sponsor. Authorship will be determined by mutual agreement. All manuscripts, abstracts or other modes of presentation arising from the results of the study must be reviewed and approved in writing by the Sponsor, prior to submission for publication or presentation. No publication or presentation with respect to the study shall be made until any Sponsor comments on the proposed publication or presentation have been addressed to the Sponsor's satisfaction.

The detailed obligations regarding the publication of any data, material results, or other information, generated or created in relation to the study shall be outlined in the agreement between each Investigator and the Sponsor or designee.

7.8 Financing and Insurance

Financing and Insurance information will be set forth in a separate document between the Investigator and Sponsor (provided by the Sponsor or designee).

7.10 Discontinuation of Study

The Sponsor reserves the right to discontinue the study for medical or administrative reasons at any time. The Investigator will be reimbursed for reasonable expenses covering subjects, use of live-in facilities, laboratory tests, and other professional fees. The Investigator will refund the excess of payments made in advance.

The Investigator reserves the right to discontinue the study should his/her judgment so dictate. The Investigator will notify the IRB in case of study discontinuation. Study records must be retained as noted above.

8 ETHICS

8.1 Institutional Review Boards / Independent Ethics Committees

A list of the Institutional Review Board(s) (IRB) and/or Independent Ethics Committee(s) (IEC) that approved this study and the approval letters will be included in the clinical study report for this protocol.

The protocol, any protocol amendments, and the informed consent form (ICF) will be reviewed and approved by the appropriate IRB before subjects are enrolled. IRB Approval is required and will be acquired prior to the distributing SM to investigational sites". The Investigators or Sponsor will submit, depending on local regulations, periodic reports and inform the IRB of any reportable adverse events (AEs) per International Conference on Harmonization (ICH) guidelines and local IRB standards of practice.

8.2 Ethical Conduct of the Study

This study will be conducted in accordance with standard operating procedures (SOPs) from either the Sponsor or [REDACTED]. These SOPs are designed to ensure adherence to GCP guidelines as required by:

- Declaration of Helsinki, 1964 ("Recommendations Guiding Physicians in Biomedical Research Involving Human Patients"), and all its accepted amendments to date concerning medical research in humans.
- ICH Guideline for GCP (Committee for Proprietary Medicinal Products/ICH/135/95) of the European Agency for the Evaluation of Medicinal Products, Committee for Proprietary Medicinal Products, ICH of Pharmaceuticals for Human Use.
- United States (US) Code of Federal Regulations (CFR) dealing with clinical studies (21 CFR, including parts 50 and 56 concerning Patient Informed Consent and IRB regulations).
- Local, national legal guidelines.

8.3 Investigators and Study Personnel

This study will be conducted by qualified Investigators under the sponsorship of Supernus Pharmaceuticals, Inc. (Sponsor) at US study sites used in the double-blind studies, 810P301, 810P302 81P503 and 810P204.

Contact persons at the Sponsor and the CROs are listed in the regulatory binder provided to each investigational site. Qualified personnel will monitor the study. Medical writing, data management, and statistical analyses will be performed by qualified service partners/CROs. Laboratory tests will be conducted by a central laboratory as designated in the regulatory binder.

8.4 Subject Information and Consent/Accent

The Investigator (or designee) will inform the subject and their parent(s), or legal representative, of all aspects pertaining to the subject's participation in the study and will provide oral and written information describing the nature and duration of the study, the procedures involved, the expected duration, the potential risks and benefits involved, and any potential discomfort.

The process for obtaining informed consent/assent will be in accordance with all applicable regulatory requirements. The Investigator (or designee) and the parent (or legal representative) must sign and date the Informed Consent Form (ICF)/Informed Assent Form (IAF) before the subject can participate in the study. The parent or legal representative and the subject will be given a copy of the signed and dated consent/assent form and the original will be retained in the investigational site study records.

The decision regarding subject participation in the study is entirely voluntary. The Investigator (or designee) must emphasize to the subject and their parent(s) or legal representative that consent regarding study participation may be withdrawn at any time without penalty or loss of benefits to which the subject is otherwise entitled.

The ICF/IAF should be given by means of a standard written statement, written in non-technical language. The subject should understand the statement before signing and dating it. If written consent is not possible, oral consent may be obtained if witnessed by at least one person not involved in the study. The verbal consent will be documented and signed by the Investigator and the witness(es). No subject can enter the study before his/her ICF has been obtained.

If the ICF/IAF is amended during the study, the Investigator must follow all applicable regulatory requirements pertaining to approval of the amended ICF by the IRB and use the amended informed consent form (including ongoing subjects).

10 APPENDICES

10.1 Retrospective Modified Overt Aggression Scale (R-MOAS)

Refer to the Investigator Site File

10.2 Clinical Global Impression (CGI) Scale

Refer to the Investigator Site File

10.3 Columbia-Suicide Severity Rating Scales (C-SSRS)

Refer to the Investigator Site File

10.4 Simpson-Angus Rating Scale

Refer to the Investigator Site File

10.5 Barnes Akathisia Rating Scale (BARS)

Refer to the Investigator Site File

10.6 Abnormal Involuntary Movement Scale (AIMS)

Refer to the Investigator Site File

10.7 Child Health Questionnaire Parent Form 28-item (CHQ-PF28)

Refer to the Investigator Site File

10.8 Parenting Stress Index-Short Form (PSI-4-SF)

Refer to the Investigator Site File

10.9 Stress Index for Parents of Adolescents (SIPA)

Refer to the Investigator Site File

# LIST OF TABLES

Table 1: Objectives and Endpoints	6
Table 2: Definitions and Derivations	8

LIST OF ABBREVIATIONS

Abbreviation	Definition
ADHD	Attention Deficit/Hyperactivity Disorder
AE	Adverse event
AESI	Adverse event of special interest
ATC	Anatomical therapeutic chemical
BMI	Body mass index
CGI-I	Clinical Global Impression – Improvement Scale
CGI-S	Clinical Global Impression – Severity Scale
C-SSRS	Columbia Suicide Severity Rating Scale
CFB	Change from baseline
CRF	Case report form
ECG	Electrocardiogram
EOS	End of Study
EPS	Extrapyramidal Symptoms
IA	Impulsive aggression
IPD	Important protocol deviation
MedDRA	Medical dictionary for regulatory activities
OLE	Open label extension
PD	Parental Distress or Parent Domain
PN	Preferred name
PSI	Parenting Stress Index
PT	Preferred term
QT	QT interval
QTcF	QT interval corrected using Fridericia's method
R-MOAS	Retrospective-Modified Overt Aggression Scale
SAE	Serious adverse event
SAP	Statistical analysis plan
SD	Standard deviation
SIPA	Stress Index for Parents of Adolescents
SM	Study medication
SOC	System organ class
TEAE	Treatment-emergent adverse event
WHO-DD	World health organization drug dictionary

#### **1. OBJECTIVES AND ENDPOINTS**

The objectives and endpoints are listed in Table 1.

rusie it objectives and Enapoints					
Objectives	Endpoints				
Safety Objective (Primary): Long-term safety on the use of SPN-810 as a treatment for impulsive aggression (IA) in subjects (6-17 years of age) with Attention Deficit/Hyperactivity Disorder (ADHD) when taken in conjunction with standard ADHD treatment only after satisfactory participation in a preceding double- blind study (810P301, 810P302,	
 
Endpoints         
 
Adverse Events
 
Extrapyramidal Symptoms (EPS) scales (Simpson-Angus Scale, Barnes Akathisia Scale, and Abnormal Involuntary Movement Scale)
 
Clinical Laboratory Tests (Hematology, Chemistry, Insulin, Prolactin and Urinalysis)
 
Concomitant Medications
 
Vital signs, Standardized BMI, Physical Examination and ECG (12- lead)
 
Columbia Suicide Severity Rating Scale (C-SSRS)
 
 
 
				
810P503 or 810P204). Efficacy Objective (Secondary): Long-term efficacy on the use of SPN-810 as a treatment for impulsive aggression (IA) in subjects (6-17 years of age) with ADHD when taken in conjunction with standard ADHD treatment.	
 
Change from Baseline (CFB) in Retrospective-Modified Overt Aggression Scale (R-MOAS) at each scheduled visit
 
Clinical Global Impression – Improvement Scale (CGI-I) at each scheduled visit
 
CFB in Clinical Global Impression – Severity Scale (CGI-S) at each scheduled visit
 
				
Quality of Life Objective (Exploratory): Long-term quality of life on the use of SPN-810 as a treatment for impulsive aggression (IA) in subjects (6-17 years of age) with ADHD when taken in conjunction with standard ADHD treatment.	
 
CFB in Child Health Questionnaire Parent Form 28-item (CHQ- PF28) at each scheduled visit
 
CFB in Parenting Stress Index – Short Form (PSI-4-SF) or Stress Index for Parents of Adolescents (SIPA) at each scheduled visit
 
Socio-demographics Characteristics
 
				

#### **Table 1: Objectives and Endpoints**

Page 6 of 25

#### 2. STUDY DESCRIPTION

#### 2.1. Study Design

Study 810P304 is a multicenter, open-label, extension study aimed to assess safety of SPN-810 in the treatment of impulsive aggression (IA) in patients aged 6-17 years with Attention Deficit/Hyperactivity Disorder (ADHD) taken in conjunction with standard ADHD treatment. The study has three phases: Optimization, Maintenance, and Taper.

All subjects who complete the randomized, double-blind portion of Studies 810P301, 810P302, 810P503 or 810P204 will have the option to participate in the open label extension (OLE) study, 810P304, in which all subjects will receive active Study Medication (SM) treatment. Subjects who choose to participate in the OLE will receive blinded conversion medication kits at Visit 6 of the previous SPN-810 double-blind randomization study (810P301, 810P302) or at Visit 4 for subjects completing the 810P204 study. Subjects, who have completed the 810P503 study and, chose to participate in this study, will receive the blinded conversion card at Visit 7.

#### 2.2. Schedule of Visits and Study Procedures

The Schedule of Events and Assessments for the study is shown in Appendix 9.1.

# 3. GENERAL CONSIDERATIONS FOR DATA ANALYSES AND HANDLING

#### 3.1. General Statistical Methods

All statistical analysis will be performed using SAS version 9.4 or higher.

All data summaries will be presented by the optimized dose group (<18 mg/day; 18-<24 mg/day, 24-<36 mg/day or 36-54 mg/day) and overall. The optimized dose is defined as the first maintenance dose (at visit 5) for subjects entering maintenance period; otherwise using the end of study (EOS) dose for subjects discontinued prior to maintenance period.

Continuous variables will be summarized descriptively using number of subjects (n), mean, standard deviation (SD), median, minimum, and maximum.

Categorical variables will be summarized descriptively using counts and percentages. However, the number of patients with missing data will be excluded from the denominator for the percentage calculation. When the denominator for the percentage is different from the number of subjects in the treatment column header, the denominator will be clearly specified in the table or in a footnote for the table.

Individual subject data will be listed by subject ID. Unscheduled measurements (unless defined as baseline) will be excluded from summary tables but will be included in data listings. For assessments that are repeated or unscheduled, unless otherwise specified, the non-missing values from the first assessment will be used for generating summary statistics.

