3.2 Overall Study Design and Plan

Study 810P304 is a multicenter, open-label, extension study aimed to assess safety of SPN-810 in the treatment of IA in patients aged 6-17 years with ADHD in conjunction with standard ADHD treatment. The study has three phases: Optimization, Maintenance, and Taper.

All subjects who complete the randomized, double-blind portion of study 810P301, 810P302, 810P503 or 810P204 will have the option to participate in the OLE study in which all subjects will receive active Study Medication (SM) treatment. Subjects who choose to participate in the OLE will receive blinded conversion medication kits at Visit 6 of the previous SPN-810 double-blind randomization study (810P301, 810P302) or at Visit 4 for subjects completing the 810P204 study. Subjects, who have completed the 810P503 study and, chose to participate in this study, will receive the blinded conversion card at Visit 7.

Visit 7 of 810P301, 810P302 or Visit 8 for 810P503 will be Visit 1 of 810P304. Visit 6 of the 810P204 will be Visit 1 of the 810P304. The initial total daily dose for the OLE is [REDACTED]
[REDACTED]

After enrollment, eligible subjects will enter an optimization phase of two to eight weeks. Subjects will return to the office for visits at weeks 2, 4 and 8 during which the SM dose may be gradually adjusted based upon tolerability or effectiveness within the limits of [REDACTED]. The Investigator may gradually increase the dose of SPN-810 up to 54 mg/day for subjects with body weight \geq 30 kg. Following optimization, subjects will return to the office at each visit (every 3 months) during maintenance phase or until the subject discontinues or the study ends. The subject may discontinue at any time if the subject or the LAR withdraws IAF or ICF or if it is no longer in the best interest of the subject, at the investigator's discretion. If the subject discontinues or is removed from the study, he/she will taper off the SM over a period of at least 2 weeks.

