3.2.5 Taper Phase (2 weeks)

All subjects who discontinue early or complete the OLE study 810P304 will taper off the study medication over a period of 2 weeks.

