4.2.8 Visit 25 [(End of Study (EOS)] (Month 60 +/- 2 weeks)

Subjects who complete the study (60 months) will be instructed to down titrate for 2 weeks before returning to the office for the EOS Visit.

This document is confidential. It contains proprietary information of Supernus® Pharmaceuticals, Inc. Any viewing or disclosure of such information that is not authorized in writing by the Sponsor is strictly prohibited. Such information may be used solely for the purpose of reviewing or performing this study.

Subjects may discontinue prior the end of the study if the subject or the LAR withdraws assent and/or consent, or if the Investigator or the Sponsor decide it is no longer in the best interest of the subject. If the decision is made to discontinue early then the subject will be contacted and instructed to down-titrate at least 2 weeks prior to the EOS Visit.

The following procedures will be performed for subjects who complete the study (60 months) or discontinue early.

1. Perform physical examination
2. Perform 12-lead ECG
3. Collect urine sample for urinalysis and urine drug screen (all subjects), and pregnancy test (FOCBP only)
4. Record vital signs (HR, BP, temperature, and RR)
5. Record height, weight and BMI
6. Collect blood samples for hematology and chemistry
7. Administer C-SSRS
8. Administer safety scales (Simpson-Angus, Barnes Akathisia, AIMS)
9. Administer efficacy scales (R-MOAS, CGI-I and CGI-S, only for subjects who discontinue early)
10. Administer quality life scales (CHQ-PF28, PSI-4-SF or SIPA, only for subjects who discontinue early)
11. Collect and assess adverse events
12. Collect SM and assess treatment compliance
13. Assess and record concomitant medications

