4.3.6 Dosing Schedule

Subjects will initiate dosing at 18 mg/day (9 mg BID) or 36 mg/day (18 mg BID) in a blinded fashion and subsequently optimized. At the Investigator's discretion, the dose may be gradually adjusted based upon tolerability and effectiveness between the doses of 6 mg/day and 36 mg/day or 54 mg/day for subjects whose body weight is \geq 30 kg. Doses should always remain BID and, whenever possible, evenly divided (same number of mg in morning and evening).

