4.6 Completion of Study and Discontinuation of Subjects

Subjects will be considered to have completed the study if they complete all visits up to and including the end of study visit. All subjects who discontinue early will be contacted by the study staff and instructed to down-titrate gradually over approximately 2 weeks prior to the EOS visit.

The Investigator(s) or subjects themselves may stop SM treatment at any time for safety or personal reasons. A subject is free to withdraw from the study at any time for any reason without prejudice to their future medical care by the physician or at the institution. The Investigator or Sponsor may also withdraw the subject at any time in the interest of subject safety. The withdrawal of a subject from the study should be discussed where possible with the Medical Monitor and/or the Investigator before the subject stops SM. Subjects removed from the study for any reason will not be replaced.

Reasons for withdrawal may include but are not limited to subject withdrawal of consent, occurrence of unmanageable AEs, or at the Investigator's discretion.

The primary reason for withdrawal must be recorded in the subject's medical record and on the eCRF. If a subject is withdrawn for more than one reason, each reason should be documented in the source document and the most medically significant reason should be entered on the eCRF.

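### SAP 3.1 groups pre-maintenance leavers by an undefined end-of-study dose, and SAP 5.1 reports adverse events with no adjustment for unequal follow-up

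*SAP*

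**What the plan says.** **Dose groups.** SAP 3.1 presents every summary by one dose group per subject and overall. The groups are below 18 mg/day and then "18-<24 mg/day, 24-<36 mg/day or 36-54 mg/day". The assignment rule has two clauses. The first covers those who reach maintenance: "The optimized dose is defined as the first maintenance dose (at visit 5) for subjects entering maintenance period". The second covers those who leave sooner: "otherwise using the end of study (EOS) dose for subjects discontinued prior to maintenance period". Neither SAP 3.1 nor the definitions table in SAP 3.2 says what the end-of-study dose is.

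**Taper.** Protocol 3.2.5: "All subjects who discontinue early or complete the OLE study 810P304 will taper off the study medication over a period of 2 weeks". Protocol 3.2 says of a subject who discontinues or is removed that "he/she will taper off the SM over a period of at least 2 weeks". Two sections place this ahead of the final visit for early leavers: "instructed to down-titrate at least 2 weeks prior to the EOS Visit" (4.2.8) and "instructed to down-titrate gradually over approximately 2 weeks prior to the EOS visit" (4.6). The synopsis, under duration of treatment, gives the taper instruction to those who have completed at least one maintenance phase.

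**Dosing.** Protocol 4.3.6: "Subjects will initiate dosing at 18 mg/day (9 mg BID) or 36 mg/day (18 mg BID"). Sections 3.2.4, 4.2.1 and 4.3.6 allow later adjustment.

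**Adverse events.** SAP 5.1 specifies TEAE tables as number and percent of subjects, each counted once per system organ class and preferred term. It uses the term incidence rates, but explains it as number and percent. SAP 4.6 summarises exposure duration by the same dose groups, in 15 categories from under 3 to at least 60 months. No person-time denominator appears in SAP 5.1 or Protocol 6.8.1.

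**The concern.** Long-term safety is the primary objective (SAP Table 1), and the by-dose TEAE tables are a main safety output. Three features affect how they can be read.

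1. An undefined term decides the column for subjects who leave before maintenance. Some of these may be early withdrawals for adverse events. Two programmers could file the same subject in different columns.
2. A percentage of subjects with an event depends on both the event rate and how long subjects were observed. With exposure allowed to vary this much, the percentages mix the two. That applies to the overall column, and between dose columns if their follow-up differs.
3. The label is fixed at Visit 5 although the dose may change afterwards, so an event may be tabulated under a dose the subject was not taking at onset.

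**Working it through.** The documents state no sample size, power or event target (Protocol 6.12), so there is no figure of the plan's own to reproduce. The first part rests on comparing passages; the second uses short arithmetic on assumed rates.

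**Who falls under the end-of-study clause.** Protocol 3.2.4 counts maintenance visits from Visit 5, and Table 1 puts Visit 4 under optimization. The clause therefore covers subjects leaving before Visit 5. From the Table 1 intervals, Visit 5 is nominally at 2 + 2 + 4 + 4 = 12 weeks. With ±1 week at each of the four intervals it falls between 1 + 1 + 3 + 3 = 8 and 3 + 3 + 5 + 5 = 16 weeks.

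**What the two readings do.** The SAP columns are <18, 18-<24, 24-<36 and 36-54 mg/day. The two initial doses are the lower edges of the second and fourth.

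| Dose before any taper | Column if the pre-taper dose is meant | Column if a reduced dose at the final visit is meant |
|---|---|---|
| 18 mg/day | 18-<24 | <18 (one column down) |
| 36 mg/day | 36-54 | 24-<36 or lower (at least one column down) |

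So for a subject still on an initial dose, any reduction changes the column. For other doses it depends on the size of the reduction. If there is no taper, the two readings coincide.

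**Effect of follow-up on a percentage.** Assume a constant first-event rate r and the same follow-up T for all subjects in a group. The expected percentage is 1 − exp(−rT). The rates are illustrative and not from the documents.

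| r per patient-year | T = 0.5 year | T = 2 years | Ratio |
|---|---|---|---|
| 0.05 | 2.5% | 9.5% | 3.85 |
| 0.2 | 9.5% | 33.0% | 3.46 |
| 0.5 | 22.1% | 63.2% | 2.86 |

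For r = 0.2: 1 − exp(−0.1) = 9.5% and 1 − exp(−0.4) = 33.0%. The event rate is identical in each row; only follow-up differs.

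**What the exposure table offers.** It shows unequal follow-up by dose group but is not used as a denominator for adverse events, and it does not give time to first event.

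**The case against.** The strongest reply is that this is a descriptive extension study with no dose-response objective. The protocol itself plans TEAE tables by optimized dose (6.8.1), and the SAP follows it. The overall column does not depend on the label, and individual data are listed. All of this stands. It is why the optimized-dose tables should stay and why a table by dose at onset is only optional. It does not define the missing term, and the overall percentages still depend on length of follow-up.

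A reader might infer more than the documents support:

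- *Early leavers will be filed at a dose of zero.* This is a strained reading: the clause defines an optimized dose, and the adjustment range in Protocol 4.3.6 starts at 6 mg/day. A partly tapered dose remains possible, which is enough to require a definition.
- *The taper passages conflict throughout.* Protocol 3.2.6 is merely silent on a taper for early leavers and directly follows 3.2.5. The Table 1 footnote on dispensing taper medication does not exclude other visits. The real tension is between the synopsis and Sections 3.2, 3.2.5, 4.2.8 and 4.6.
- *Most follow-up is at the wrong dose.* The share of follow-up after Visit 5, (T − 3)/T in months, is 50% for a 6-month stay and 95% for 60 months. That is time after the label is set, not time at another dose. Protocol 4.2.1 also expects subjects to continue on their optimized dose.
- *The exposure table can correct only rare events.* With a constant rate and equal follow-up within a column, −ln(1 − p)/T recovers the rate exactly: −ln(1 − 0.330)/2 = 0.20. With unequal follow-up within a column this is approximate, but no limit to rare events follows.

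**Conclusion.** The point holds in three parts of different weight. First, the end-of-study dose is undefined. On a literal post-taper reading, subjects leaving before Visit 5 move to a lower column if they were on an initial dose, and may move otherwise. The documents do not show how many are affected. Second, TEAE percentages without person-time mix risk with follow-up. In the illustration, identical rates differ by a factor of about 2.9 to 3.9 between 6 and 24 months. Columns are distorted relative to each other only if their follow-up differs, which cannot be known from the plan. Third, the label may differ from the dose at onset, with unknown frequency; this calls for a footnote, not a redesign.

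The documents do not support a claim that dose comparisons are biased in a known direction or by a known amount. The changes are still worth making, because they are specific and cheap and concern the primary objective.

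**What to change.** 1. **SAP 3.1.** For subjects who discontinue before maintenance (before Visit 5) only, replace the end-of-study dose with the last prescribed dose before any taper. Leave the first-maintenance-dose rule unchanged for everyone else, so that a subject who misses Visit 5 but stays is not relabelled by a much later dose. This wording works however the taper passages are reconciled, and the sponsor should reconcile them.
2. **SAP 5.1.** Add exposure-adjusted first-event rates (subjects with a first event per patient-year at risk) for TEAEs, SAEs, AESIs and withdrawals due to adverse events, overall and by optimized-dose group. Use one at-risk window for numerator and denominator, for example to the earlier of first onset and the end-of-study or last visit. SAP 5.1 treats every adverse event reported in the study as treatment-emergent, so stopping the clock at last dose would leave later events without matching time. Keep the number-and-percent tables.
3. **By-dose tables.** Footnote them as descriptive, with a label that may differ from the dose at onset. A table by instructed dose at onset is optional; exact dates of dose changes between visits may be lacking.

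The cost is SAP wording and modest extra programming. Items 1 and 2 use data the study already collects. The main limitation is that a single rate per patient-year assumes a roughly constant hazard.
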